### **Secondary:**

- Evolution of Gas-exchange, Hemodynamics, and Respiratory Mechanics during the Study Intervention Period.
- Ventilator Free Days during days 1-28 and 1-60 post-randomization (defined as in reference 5).
- Organ or System Failure Free Days during days 1-28 and 1-60 post-randomization (organ failures will be defined on the basis of a corresponding sequential organ dysfunction assessment score of 3 or 4).
- Occurrence of Barotrauma (i.e., any new pneumothorax, pneumomediastinum, or subcutaneous emphysema, or pneumatocele > 2 cm).
- Occurrence of Tracheal Mucosal Injury due to use of TGI.

### **Power Analysis and Study Periods**

Based on pilot data, we estimate an absolute HFO-TGI related improvement of 26% in the survival to hospital discharge. For the determination of a 26% absolute difference in hospital mortality with alpha=0.05 and power=0.80, a total sample size of 124 patients will be required.

Based on pilot data, we wish to provide the following estimates for the study: 1) a minimum investigator-to-patient ratio of 1:1 for days 1-10 post-randomization (i.e. the intervention period): 2 investigators have to be assigned to each patient of each group on a rotating 12-hour basis to apply either the HFO-TGI protocol, or the lungprotective CMV strategy, and the RM protocol of the CMV group; in each 12-hour study shift, each investigator may apply the study protocol in up to 2 patients simultaneously; 2) for days 1-10: in Evaggelismos hospital, 1 of the 3 supervising investigators will be available on a rotating basis for advice and/or assistance with respect to the application of the study protocol; 3) a minimum investigator-to-patient ratio of 1:3 for day 11 to hospital discharge: 1 investigator will be concurrently assigned to a maximum of 3 patients for daily collection of the follow-up data and confirmation of the application of the standardized lung-protective CMV strategy, and/or application of the weaning protocol; 4) a maximum and average predicted enrollment rate for Evaggelismos hospital of 6 and 4.2 patients per month, respectively; 5) a maximum predicted concurrent presence of 3 patients in the intervention period and 6 patients in the post-intervention follow-up period, requiring a total of 5 assigned investigators; 6) a projected temporary reduction in the actually available investigator manpower of 7 (with supervising investigators included) of Evaggelismos hospital to 5 in-between October 2007 and February 2008; 7) a maximum and average predicted enrollment rate for Larissa hospital of 2 and 1 patients per month, respectively, requiring at least 2 investigators; and 8) a requirement of ≥50 hours of prior, principal investigator-guided use of HFO-TGI for each one of the investigators of the Larissa hospital (50 hours correspond to approximately 50% of the average time of HFO-TGI use per investigator during the pilot period). The predictions for Evaggelismos hospital were based on organization experience gained from the period of the pilot data collection. The predictions for Larissa hospital were based on the 1.0:3.7 bed ratio of its ICU vs. the ICU of Evaggelismos.

After considering the above-mentioned factors of study feasibility, we propose to conduct the trial in 2 periods: a single-center first period of at least 50 patients (average estimate=52 patients, maximum=54 patients), starting on July 2006 and having a projected duration of 12-13 months; and a two-center final period of at least 70 patients, starting on March 2008 and having a projected duration of 14-15 months.

# First study period planning

An interim analysis assessing safety data will be conducted after the enrolment of 20 patients. Following the (probable in our opinion) establishment of patient safety, we will be able to extend the study until the enrolment and follow-up completion of 50-54 patients. Based on our pilot period data, we have estimated an HFO-TGI-related improvement in compliance of 25% within days 5-10 (improvement most likely to be confirmed within days 5-8). For alpha = 0.05 and power = 0.80, we will have to enroll 52 patients, whereas the enrollment of 54 patients will raise power to 0.82." Consequently, provided that our pilot data-based prediction is confirmed in the first 20 participants of the first study period, we will conclude that this study period will be adequately powered to assess the evolution of respiratory physiology during

[figure not shown]
the study intervention period. As according to our original hypothesis the evolution of respiratory physiology is a prerequisite for an HFO-TGI-associated improvement in survival, following the aforementioned confirmation, we will add this "intermediate" outcome to the (registered with Clinicaltrials.gov) primary outcome measures of the first study period.

The other primary outcome measure for the first study period will be (as for the whole study) survival to hospital discharge; additional survival assessment time points may include days 28 and 60 post-randomization. The current study period will not be sufficiently powered to reliable assess in-hospital mortality. Nevertheless, regarding 28-day survival, a possible, large chi-square effect size of 0.5-0.6 would result in alpha ≤0.04 and power ≥0.81. This will correspond to a between-group, 28-day survival difference similar to that determined in the Amato trial [i.e. 34% (26)]. However, in such a case, a large difference in 28-day survival will also likely be reflected by a concurrent difference in ventilator-free days (26), which in turn will be explained by early improvements in the respiratory physiology of the HFO-TGI group. Regarding the potential for TGI-associated tracheal mucosal damage (14), this will be assessed as feasible (feasibility to be confirmed during the first period) according to the pre-specified grading of Table 2.

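### Compliance becomes a first-period primary outcome only if its effect is confirmed in the first 20 patients, whose data are then reused to test it; the rule is undefined and cannot show adequate power

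*Protocol*

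**What the plan says.** All of this stands in the Protocol, First study period planning, unless noted.

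- The look: "An interim analysis assessing safety data will be conducted after the enrolment of 20 patients". Once safety is established, the investigators may "extend the study until the enrolment and follow-up completion of 50-54 patients".
- The planning assumption: "we have estimated an HFO-TGI-related improvement in compliance of 25% within days 5-10". The size follows: "For alpha = 0.05 and power = 0.80, we will have to enroll 52 patients", and "the enrollment of 54 patients will raise power to 0.82".
- The condition: "provided that our pilot data-based prediction is confirmed in the first 20 participants of the first study period". If it is met, the protocol draws two consequences. The first period is judged to have enough power for respiratory physiology, and that outcome joins the "outcome to the (registered with Clinicaltrials.gov) primary outcome measures of the first study period".
- Without promotion, respiratory mechanics is a secondary outcome (Outcome Measures, Secondary). Survival to hospital discharge is primary in either case.

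The protocol gives no threshold, test or single day for confirmation. It does not set the first 20 patients apart in the later analysis.

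**The concern.** The prediction is a difference attributable to HFO-TGI, so it can be confirmed only by comparing the arms. Three problems follow.

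1. **Selection and reuse.** A favourable early difference decides that the outcome is primary, and the same difference then contributes 20 of about 52 patients to its test. Among trials in which promotion happens, the estimate and p-value lean towards benefit.
2. **A wrong inference about power.** An observed effect in 20 patients does not show that 52 are enough. A chance high value would pass as proof, and a chance low value would count against a sound design.
3. **An open rule.** The window runs over days 5-10, with days 5-8 thought most likely. Those who have seen the data would decide what counts as confirmation.

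The protocol concedes that the first period lacks power for in-hospital mortality and calls the physiological change a prerequisite for a survival benefit. The promoted outcome would therefore carry much of the first-period report.

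**Working it through.** **Inputs from the protocol:** 25% improvement; alpha 0.05; power 0.80 at 52 patients and 0.82 at 54; look at 20 patients.

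**Assumptions:** two-sided test; 1:1 allocation (10 per arm at the look, 26 at the end); normal data. The SD of compliance is not given, so the standardised effect d is solved backwards from the stated size.

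**Step 1: reproduce the plan's figures.** Power comes from the noncentral t with noncentrality d·√(n/2), where n is the number per arm.
- n=26, power 0.80: d = 0.792. The implied SD is 25%/0.792 = 31.6% of control compliance.
- n=27: 0.792·√13.5 = 2.91, power 0.815, against 0.82 stated. The plan's two figures agree to rounding.

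**Step 2: what 20 patients can show.** n=10: 0.792·√5 = 1.77, power 0.39.

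**Step 3: bias of the promoted estimate when confirmation means an observed effect of at least 25%.** The interim estimate has SE √(2/10) = 0.447 SD units and carries weight 10/26 in the final estimate.
- No true effect: the threshold lies 0.792/0.447 = 1.77 SE above zero, so P(promoted) = 0.038. The mean interim estimate given promotion is 0.447 × 2.17 = 0.97. Final mean: 0.97 × 10/26 = 0.37 SD, and 0.37 × 31.6% ≈ 12% improvement.
- True 25% effect: P(promoted) = 0.50. The mean interim excess is 0.447 × 0.798 = 0.357. Final excess: 0.357 × 10/26 = 0.137 SD, about 4.3 points, so the mean estimate is about 29.3%.

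**Step 4: other meanings of confirmation.** Simulation of patient-level data with t-tests, 800,000 trials per scenario. Significant means two-sided p<0.05 in favour of HFO-TGI at 52 patients.

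No true effect:

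| Confirmed means | P(promoted) | False positive given promotion | Unconditional false positive | Mean estimate given promotion |
|---|---|---|---|---|
| p<0.05 at 20 patients | 0.025 | 24% | 0.6% | 12% |
| observed effect ≥25% | 0.038 | 21% | 0.8% | 12% |
| ≥18.75% | 0.092 | 15% | 1.3% | 10% |
| ≥12.5% | 0.188 | 10% | 1.9% | 8% |
| any positive difference | 0.50 | 5% | 2.4% | 4% |

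True 25% effect:

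| Confirmed means | P(promoted) | P(promoted and significant) | Mean estimate given promotion |
|---|---|---|---|
| p<0.05 at 20 patients | 0.39 | 0.37 | 30% |
| observed effect ≥25% | 0.50 | 0.47 | 29% |
| ≥18.75% | 0.67 | 0.61 | 28% |
| ≥12.5% | 0.81 | 0.71 | 27% |
| any positive difference | 0.96 | 0.79 | 25.5% |

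The comparators, with the outcome fixed in advance, are 2.5% false positives in this direction and power 0.80. A normal approximation (d = 0.777) gives 0.39 in place of 0.37 and 26% in place of 24% for the first rule, and 0.47 and 22% for the second.

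**Step 5: setting the first 20 aside.** The 32 later patients (n=16) give 0.792·√8 = 2.24 and power of about 0.58.

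**The case against.** The strongest reply is that little is lost. Compliance falls under a planned secondary outcome, and continuing to 50-54 patients is tied to safety, not to the compliance result. The comparison on about 52 patients can therefore be made either way, and only its label depends on the look. The conditional change is announced in advance with a reason, and the 124-patient survival analysis is untouched. All of this stands, and it limits the point.

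Four stronger readings are tempting but unsupported.

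- **Power falls from 0.80 to 0.47.** That is the result of one rule, an observed effect of at least 25%. It is the most literal reading of confirming a 25% prediction, but the protocol does not state it. The figure is also the chance of being primary and significant together, not the power of the comparison.
- **Type I error is inflated.** Unconditionally it is not. The rate in favour of HFO-TGI stays at or below 2.5% under every rule, because promotion is an added hurdle. The distortion applies to results that were promoted.
- **A safety-only look is being broken.** The protocol says the look assesses safety data. It does not say only safety data, nor that the compliance check is part of that analysis.
- **A second primary is tested at full alpha.** Both sample-size statements use 0.05, but the protocol states no allocation, and the SAP, not available here, may contain one.

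The objection does not answer the selection and reuse of the same data, the undefined rule, or the inference about power. A SAP could define the rule, but the data-dependent promotion is fixed in the protocol itself.

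**Conclusion.** The point holds in this form: the status of a primary outcome depends on comparative efficacy data that are then used again to test it, under a rule that is not defined, and the confirmation is wrongly read as evidence of adequate power.

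The size depends on what confirmation means. Given promotion and no true effect, the false-positive rate is about 5% to 24% against 2.5%, with a mean apparent improvement of about 4% to 12%. With a true 25% effect, the promoted estimate averages about 25.5% to 30%, and compliance ends as a significant primary outcome with probability 0.37 to 0.79 against 0.80. At the lenient end the cost is small; under the literal 25% rule it is not.

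These figures rest on 1:1 allocation, a two-sided test, and an effect size back-solved from 52 patients. The loss is one of primary status and of a fair reading of the promoted result, not of the compliance comparison or the survival analysis.

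**What to change.** Before any comparative look, and whatever it shows, choose one of two options:

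- name compliance a first-period primary outcome, as one summary over one fixed day window, with a stated share of alpha beside survival; or
- keep it secondary.

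In either case:

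- restrict the 20-patient look to safety;
- if the planning assumption must be checked, use only the pooled SD of compliance without arm labels;
- delete the statement that confirmation in 20 patients shows adequate power.

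The cost is wording in First study period planning and a matching registry entry, with no added procedures. If compliance takes a share of alpha below 0.05, its power at 52 patients falls below 0.80 and the size needs rechecking. The small downside is losing the option to choose the endpoint after the look. Keeping the promotion rule but testing only the 32 later patients would remove the reuse, but with power of about 0.58, so it is the weaker remedy.

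### If physiology is promoted after the first 20 patients, period 1 has two primary outcomes, with compliance sized at the full 0.05 and no alpha split, testing order or success rule

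*Protocol*

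**What the plan says.** In the protocol's Outcome Measures, survival (days 28 and 60, and to hospital discharge) is primary, and the evolution of gas exchange, hemodynamics and respiratory mechanics is secondary. First study period planning changes this for the first 50-54 patients, on a condition: "provided that our pilot data-based prediction is confirmed in the first 20 participants of the first study period". If it is met, "we will add this 'intermediate' outcome to the (registered with Clinicaltrials.gov) primary outcome measures of the first study period". The reason given is that "the evolution of respiratory physiology is a prerequisite for an HFO-TGI-associated improvement in survival".

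The section then names the second primary: "The other primary outcome measure for the first study period will be (as for the whole study) survival to hospital discharge". It adds that "additional survival assessment time points may include days 28 and 60 post-randomization".

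On error levels, the period is sized for a 25% improvement in compliance within days 5-10: "For alpha = 0.05 and power = 0.80, we will have to enroll 52 patients". No period-1 level is given for survival to discharge, and the section says period 1 is not sufficiently powered for in-hospital mortality. The only alpha attached to hospital mortality is the 0.05 for the 124-patient study, in Power Analysis and Study Periods. For 28-day survival, the section says that a large "chi-square effect size of 0.5-0.6 would result in alpha ≤0.04 and power ≥0.81".

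**The concern.** Two primary outcomes in the same patients need a rule for what counts as success. Here one of them takes the whole 0.05, the other has no stated period-1 level, and nothing says whether one significant result is enough, whether both are needed, or which is tested first. A period-1 report could therefore claim a positive primary on physiology alone or on survival alone. A survival claim with unchanged physiology would also be hard to read, because the protocol makes physiology the route to a survival gain.

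The promotion step adds a second difficulty. The 20 patients who decide whether physiology becomes primary are among the 52 in whom it is then tested, and the protocol does not say what result would confirm the prediction.

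**Working it through.** **Inputs.** From the protocol: 52 or 54 patients, alpha 0.05, power 0.80 or 0.82, a 25% compliance improvement, and a decision after 20 patients. Assumed, because not stated: 1:1 allocation, two-sided tests, survival tested at 0.05, either result sufficient, normal approximation, and no true effect on either outcome.

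**1. The protocol's own figure.** The section states "For alpha = 0.05 and power = 0.80, we will have to enroll 52 patients, whereas the enrollment of 54 patients will raise power to 0.82". No standard deviation is given, so 52 cannot be derived, but the implied standardised effect can be solved from it:

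d = (1.960 + 0.842) × √(2/26) = 0.777, which is a standard deviation of 0.25/0.777 = 32% of the control mean.

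At 27 per arm, power = Φ(0.777 × √(27/2) − 1.960) = Φ(0.895) = 0.815, close to the stated 0.82. The two figures agree with each other, and both use the full two-sided 0.05.

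**2. Two tests at 0.05, ignoring the promotion step.** If independent, 1 − 0.95 × 0.95 = 9.75%. For correlated tests, P(|Z1| > 1.96 or |Z2| > 1.96) from the bivariate normal is:

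| Correlation | 0 | 0.3 | 0.5 | 0.7 | 0.8 |
|---|---|---|---|---|---|
| Error | 9.8% | 9.5% | 9.1% | 8.4% | 7.8% |

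**3. With the promotion step.** Simulation (4 million draws per correlation), with the first 20 patients (10 per arm) counted among the 52. The standard error of the difference at 20 patients is √(2/10) = 0.447 SD. The chance of promotion under the null is therefore 0.50 if confirmed means any favourable difference, 1 − Φ(0.389/0.447) = 0.19 if it means at least half the predicted effect, and 1 − Φ(0.777/0.447) = 0.04 if it means the full effect. Compliance counts as a primary only when promoted.

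| Meaning of confirmed | P(promoted) | P(false compliance result, given promotion) | Either false, overall (corr. 0 / 0.5) | Either false, given promotion (corr. 0 / 0.5) |
|---|---|---|---|---|
| Any favourable difference | 0.50 | 0.050 | 7.4% / 7.0% | 9.7% / 9.1% |
| At least half the effect | 0.19 | 0.100 | 6.8% / 6.5% | 14.5% / 14.3% |
| The full effect | 0.04 | 0.220 | 5.9% / 5.7% | 26% / 26% |

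Hand check of the middle row, independent case: given promotion, 1 − 0.900 × 0.95 = 14.5%. Overall, 1 − (1 − 0.193 × 0.100) × 0.95 = 6.8%. A stricter criterion lowers the overall rate because promotion is rarer. It raises the rate given promotion because the same 20 patients are used again.

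**4. Could a later document simply split alpha?** At 0.025 for compliance, power at 52 patients is Φ(0.777 × √13 − 2.241) = Φ(0.560) = 0.71, and at 54 it is 0.73. For power 0.80, n per arm = 2 × (2.241 + 0.842)²/0.777² = 31.5, so 64 patients in all. The stated maximum for the first period is 54.

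**5. The 0.04.** With 52 patients and an effect size of 0.5 (one degree of freedom), power is 0.94 at alpha 0.04 and 0.95 at alpha 0.05. Alpha is an input to this calculation, so it cannot result from the effect size. The phrase does not allocate 0.04 to survival, and 0.04 is not used above.

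**The case against.** The strongest reply is that this is an absence. Multiplicity rules are commonly left to a statistical analysis plan, and that plan is not at hand. This would settle the matter if the protocol left the question open. But the protocol itself names both primaries, adds one during the period and fixes the sample size at an undivided 0.05. Step 4 shows that a later even split would not fit that sample size. A fixed sequence or a both-required rule would fit, so the choice has to be made where the number is set.

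A reader might infer that the text commits period 1 to an 8-10% error rate. It does not. The protocol never says that one significant outcome suffices. If both were required, there would be no inflation. The promotion step also brings the overall null rate down to about 6-7%. Both objections stand against the stronger reading. What remains is that the text does not exclude the either-result reading, and that the lower figure averages over trials in which physiology never became primary.

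A reader might also take 0.04 as a second allocated alpha. It belongs to an optional time point under a hypothetical large effect, so that reading fails.

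It can fairly be added that survival and physiology are different claims, and that placing survival behind a whole-study secondary outcome is partly a design preference. The protocol's own causal order and its statement on power for in-hospital mortality support that preference in period 1. They do not make it the only possible choice.

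**Conclusion.** The concern holds in a limited form. If physiology is promoted, period 1 has two primary outcomes in the same 50-54 patients, one sized at the full 0.05, with no split, order or success rule.

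If each is tested at two-sided 0.05 and either may support a claim, the false-positive rate under the null is:

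- about 8-10% ignoring the promotion step (correlation 0 to 0.7);
- about 6-7% overall with it;
- about 8-10% or higher once physiology has been promoted, the excess depending on the undefined criterion.

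These figures illustrate what the silence allows; they are not rates the protocol states. They cover physiology and one survival endpoint only. Testing days 28 and 60 at 0.05 as well would give about 14-15% without the promotion step, for assumed survival rates of 40-70%. The repeat survival test at 124 patients is a separate matter. The change should be made, and it is one of wording.

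**What to change.** In First study period planning, state for period 1:

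1. Compliance, at one named time point or as one named summary within days 5-10, is tested first at two-sided 0.05.
2. Survival to hospital discharge is the single survival endpoint and may be claimed at 0.05 only if compliance is significant.
3. Otherwise, and for days 28 and 60 in every case, period-1 survival is reported as an estimate with a confidence interval and no significance claim.
4. The same rule applies whether or not physiology is promoted, so that the promotion decision does not alter the error rate. If instead survival were tested alone at 0.05 whenever promotion failed, the error with the half-effect criterion would be 0.193 × 0.100 + 0.807 × 0.05 = 6.0%.
5. The 28-day sentence is reworded so that alpha is a preset level and power is what follows from the effect size.

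This holds the two-outcome error for period 1 at or below 5%, keeps 52 patients and power 0.80 for compliance, and follows the protocol's own prerequisite logic.

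The cost is that period 1 can make no stand-alone survival claim if compliance fails, including when physiology was never promoted. Naming one compliance measure also narrows the promoted outcome, which is now worded as the evolution of respiratory physiology. The remaining physiologic measures would be reported as supportive.

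### Survival to hospital discharge is primary for the first period and again for the whole study that contains it, with no share of alpha or descriptive label for the first comparison

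*Protocol*

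**What the plan says.** The protocol's Power Analysis and Study Periods section bases the whole study on a pilot estimate: "we estimate an absolute HFO-TGI related improvement of 26% in the survival to hospital discharge". It concludes that "with alpha=0.05 and power=0.80, a total sample size of 124 patients will be required". The same section divides the trial into "a single-center first period of at least 50 patients", with an average of 52 and a maximum of 54, followed by "a two-center final period of at least 70 patients". The two periods together make up the planned total, so the first-period patients are part of the final sample.

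Under First study period planning, the first period has its own endpoint: "we will be able to extend the study until the enrolment and follow-up completion of 50-54 patients". It also has its own primary outcomes. One is a respiratory physiology outcome, to be added if the first 20 patients bear out the pilot prediction. For the other, the text reads "The other primary outcome measure for the first study period will be (as for the whole study) survival to hospital discharge". The level of 0.05 given in this section belongs to the compliance calculation: "For alpha = 0.05 and power = 0.80, we will have to enroll 52 patients". No test level is given for first-period survival to discharge. The section concedes that the first period lacks the power to assess in-hospital mortality reliably. The only analysis it calls interim is the safety review after 20 patients.

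**The concern.** Followed as written, the plan yields two primary comparisons of one hypothesis on nested data: one on about 42% of the patients (52/124) and one on all of them. The 124 is a single-test calculation at the full 0.05, with no allowance for an earlier test. Nothing says that the first comparison is only an estimate, and the word primary suggests otherwise.

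What is at stake is a mortality claim. A chance survival difference among 52 patients could be published as a positive primary result, and a second test at the full level would still follow. An early positive report could also affect equipoise and recruitment in the second period. The low power of the first period does not reduce the false-positive risk; it means that a significant result there would tend to overstate the effect.

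**Working it through.** **Inputs.** From the protocol: N = 124 (at least 50 + 70 = 120), alpha 0.05, power 0.80, a 26-point absolute difference, and a first period of 50 to 54 patients, 52 on average. Assumed, because not stated: two-sided tests, 1:1 allocation, and 0.05 as the first-period level for survival to discharge. That is the only alpha given for this endpoint, and it is attached to the 124-patient calculation.

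**1. The plan's own 124.** The control rate is not given, so I scanned control survival from 1% to 72% with the usual two-proportion formula. Without a continuity correction, the two-sided total never exceeds 114. With the correction it is exactly 124 at control survival of about 26–27% or 47–48%. The figure is therefore attainable and is not shown to be wrong. It is a one-test calculation that uses the whole 0.05.

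**2. Two nested tests at 0.05.** Under the null hypothesis the first-period and final statistics Z1 and Z2 are approximately bivariate normal, with correlation

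ρ = √(n1/N) = √(52/124) = √0.419 = 0.648.

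The chance of at least one false-positive result is

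P(|Z1| > 1.96 or |Z2| > 1.96) = 1 − P(|Z1| ≤ 1.96 and |Z2| ≤ 1.96) = 0.0857.

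Put another way, each test contributes 5% and both are falsely positive together in about 1.43% of trials: 5% + 5% − 1.43% = 8.57%. The figure for independent tests, 1 − 0.95² = 9.75%, does not apply, because the data overlap.

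**3. Sensitivity.**

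| Case | Chance of at least one false positive |
|---|---|
| 52 of 124 | 8.57% |
| 50 of 124 | 8.62% |
| 54 of 120 | 8.48% |
| First period at 0.04, final at 0.05 | 7.8% |
| Both one-sided at 0.05 | 8.3% |
| Two-sided, favouring HFO-TGI only | 4.3% (nominal 2.5%) |
| Uncorrected chi-square, simulated at 40–60% survival | 8.9–9.2% |

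The row of 4.3% is 1 − P(Z1 ≤ 1.96 and Z2 ≤ 1.96) = 0.0429.

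**4. Boundaries that restore 5% at 52/124.**

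- Haybittle-Peto: p < 0.001 in the first period leaves a final nominal level of 0.0497.
- Lan-DeMets spending of O'Brien-Fleming type: p < 0.0011 leaves 0.0496.
- Equal (Pocock-type) levels: 0.0285 at each analysis. With the continuity correction, a fixed-sample calculation at that level needs about 142 patients.

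**5. Cost in power.** A test with 80% power at two-sided 0.05 has a standardised effect of 1.960 + 0.842 = 2.802. At a final level of 0.0497 or 0.0496, power is 79.9%. At the control rates that reproduce 124, the required total at 0.0496 is still 124.

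**The case against.** The strongest reply is that the protocol never says that first-period survival to discharge will be tested at 0.05. The level is inferred, and a statistical analysis plan that is not shown could divide alpha. No stopping rule hangs on the result: the second period has a planned start of March 2008, and the feasibility estimates link the interval before it to investigator availability. If the second period runs regardless, the 124-patient test keeps its 5% error. The protocol also admits that the first period is underpowered for in-hospital mortality.

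Most of this stands, and it limits the point. The 8.6% is conditional on the assumed levels, and it measures the chance of at least one false result across two reports. A reader might infer that the stated 0.05 is simply wrong for the final test. The documents do not support that, because 0.05 is stated for the 124-patient calculation alone.

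A reader might also take the remark on 28-day survival, with an alpha of at most 0.04, as a planned early survival claim. It is a conditional statement about power for a possible large effect, on a different endpoint, and not a decision rule. Nor can a larger error rate be stated by adding days 28 and 60: the protocol says only that these time points may be assessed in the first period, and it gives no mortality rates from which to compute one.

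The reply does not remove what the protocol itself fixes: the same primary outcome twice, nested samples, a final test sized at the full alpha, and no descriptive label for the first comparison. Low power is no protection against a false positive.

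**Conclusion.** The point holds in conditional form and should be fixed. If survival to discharge is tested at two-sided 0.05 both in the first period and at the end, the chance of at least one false-positive result is about 8.6% (8.5–8.6% for 50–54 of 120–124 patients), or 7.8% if the first period used 0.04. For false claims in favour of HFO-TGI it is about 4.3% against 2.5%. These figures rest on the assumed first-period level, two-sided tests and 1:1 allocation, and they cover this one endpoint. The final test is sound on its own only if no survival claim or decision is drawn from the first period, and the protocol does not say that none will be. The 20-patient safety review is not part of the problem.

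**What to change.** Under First study period planning, state that first-period survival to discharge is reported as an estimate with a confidence interval and without a significance claim, and that the 124-patient test is the only confirmatory survival test. That is enough, and it leaves the final level and the sample size unchanged.

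If a first-period survival claim is wanted, declare the comparison an interim efficacy look of the 124-patient trial and fix its boundary before any first-period survival data are seen. Examples are Haybittle-Peto p < 0.001 with a final nominal level of 0.0497, or Lan-DeMets O'Brien-Fleming-type p < 0.0011 with 0.0496. The cost is about 0.1 percentage point of final power, with no change to the 124.

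Under either choice, the first period can no longer claim survival significance at p < 0.05.
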